Incidence of AF will be determined from device data, and the endpoint for the primary analysis will be the first day after randomization on which there is >6 hrs of AF reported in the device's Cardiac Compass Trends. The analysis will compare incidence of AF using survival analysis methods. As secondary analyses device measured AF burden and treatment for AF will be analyzed.

To test the hypothesis that the change in quality of life, measured by the KCCQ, in the aCRT ON group is better than the change in the aCRT OFF group.

The parameter of interest is the KCCQ overall summary score (range, 0 to 100; higher scores indicate better health status) which will be assessed at baseline and at the 3, 6, 12, 18, and 24 months follow-up visits. The summary score at the follow-up visits will be analyzed using a linear mixed effects regression model that will account for the correlation of scores within each patient. The treatment arm allocation will be included as a main effect. The baseline KCCQ score as well as the stratification variables included in the primary objective model will be included as covariates in the model. Analysis will be corrected for time trends if needed.

To test the hypothesis that the change in health outcome, measured by the EQ-5D, in the aCRT ON group is better than the change in the aCRT OFF group.

The parameter of interest is the EQ-5D index, which will be assessed at baseline and at the 3, 6, 12, 18, and 24 months follow-up visits. Derivation of the index will follow instructions provided by the EuroQol Group (www.euroqol.org). The index at the follow-up visits will be analyzed using a linear mixed effects regression model that will account for the correlation of measurements within each patient. The treatment arm allocation will be included as a main effect. The baseline EQ-5D index as well as the stratification variables included in the primary objective model will be included as covariates in the model. Analysis will be corrected for time trends if needed.

To test the hypothesis that aCRT reduces the incidence of all-cause re-admissions after a heart failure (HF) admission within 30-days of the index event.

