the event or the date of last documented follow-up since randomization for those who are censored. Date of last documented follow-up since randomization is the maximum value among the dates of randomization, randomization programming, any study scheduled follow-up visit, exit, adverse event onset, adverse event resolved, system modification, and healthcare utilization. Rand is an indicator variable for randomized treatment groups (1=aCRT ON, 0=aCRT OFF).

The hazard ratio for treatment arm (aCRT ON) versus control arm (aCRT OFF) will be reported with its associated p-value and 95% confidence interval. The null hypothesis will be rejected when the p-value is below the critical value for the (interim or final) analysis. The actual cumulative α level will be calculated based on the actual number of primary events included in each interim analysis. The estimated cumulative α -level is approximately 0.00002, 0.00304, 0.0193 and 0.05 at the 1st interim with 275 events, 2nd interim with 550 events, 3rd interim with 825 events and the final analysis with 1100 events, respectively (see details in section 0). It will be concluded that aCRT reduces the incidence of the primary endpoint when the null-hypothesis is rejected and the hazard ratio is below 1. Kaplan-Meier plots for incidence of primary endpoint will be presented by treatment arms, for all patients and for the separate NYHA class groups. The absolute event rate difference at 2 years post randomization will also be calculated.

The following model assumptions will be checked:

1. Proportional hazards between treatment arms: an interaction term of treatment arm by time (in log scale) will be added into the model (see the code below). If this interaction effect is not significant, the proportional hazard assumption holds. Otherwise, this interaction term should be kept in the model as a remedy for non-proportional hazards, and any secondary analysis where treatment (or treatment by subgroup factor interaction) is included should also include the corresponding interaction term with time. Being time dependent, the treatment effect will be assessed every 6 months to the end of the follow-up to monitor the direction. Significance of the treatment effect will be based on its estimate at 24 months using a contrast.

```
PROC PHREG DATA=primary;  
  CLASS NYHA site;  
  MODEL time*event(0) = rand rand_t / TIES=efron;  
  rand_t = rand*log(time);  
  STRATA NYHA;  
  RANDOM site/ dist = gamma;  
RUN;
```

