where TtoHFevent starts from the date of randomization and ends at the date that the first HF event occurs for those who experience the HF event, or the date of death for those who died before experiencing a HF event, or the date of last documented follow-up for those who are censored. HFeventCens = 0 when a subject did not experience a HF event or death and therefore was censored; HFeventCens = 1 when a subject experienced a HF event the first time since randomization; HFeventCens = 2 when a subject died without experiencing a HF event. The competing risk exists when HFeventCens = 2.

The hypothesis regarding the aCRT effect on HF event will be tested using a Cox proportional hazards regression model with a random site effect (frailty), stratified by NYHA class at enrollment. Section 4.3.2 has described this model in details. The analysis will be conducted using code similar to:

```
PROC PHREG DATA=HFevent;  
  CLASS NYHA site;  
  MODEL time*HFevent(0) = rand / TIES=efron;  
  STRATA NYHA;  
  RANDOM site/dist = gamma;  
RUN;
```

In these codes, HFevent = 1 if a subject experienced a HF event and HFevent = 0 otherwise; time to HF event starts from the date of randomization and ends at the date that the first HF event occurs for those who experienced at least one HF event, or the date of last documented follow-up or date of death for those who are censored. Date of last documented follow-up since randomization is the maximum value among the dates of randomization, randomization programming, any study scheduled follow-up visit, exit, adverse event onset, adverse event resolved, system modification, and healthcare utilization.

The model assumptions will be checked using the same methods that are described in detail in section 4.3.2 for the primary endpoint. That is, the assumption of proportional hazards between the treatment arms will be checked by testing the significance of treatment by time interaction term; and, the assumption of constant hazard ratio for treatment across NYHA classes will be checked by testing the significance of treatment by

NYHA class interaction and evaluating the hazard ratio for treatment within each NYHA class.

Missing Data

Non-informative censoring is assumed for lost to follow up in the analysis of intervention for heart failure decompensation

Secondary Competing Risk Analysis: Fine-Gray Regression

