4.4.4 Secondary Objective #4: Incidence of atrial fibrillation (AF)

The secondary objective #4 is to test the hypothesis that aCRT ON reduces the incidence of AF compared to aCRT OFF.

Hypothesis

Occurrence of AF will be recorded in device data. The endpoint will be the first day after randomization on which there is >6 hrs of AF reported in the device's Cardiac Compass Trends.

Considering the presence of death as a competing risk, the cumulative incidence function of AF event in the treatment arm, $F_T(t)$, and control arm, $F_C(t)$, are the proportion of patients that have had the first >6 hrs AF episode prior to time t .

In the primary analysis, Cox regression will be used for competing risk analysis where only the hazard of the event of interest is modeled and there is no simple connection between covariate effect from Cox model and cumulative incidence curves.

Let $h_T(t)$ and $h_C(t)$ be the associated hazard functions. Under the Cox regression model, $h_T(t) = HR \cdot h_C(t)$, where HR is the hazard ratio of treatment compared to control for occurrence of the first >6 hrs AF episode. The null and alternative hypotheses can be expressed as:

$$H_0 : HR = 1$$

$$H_A : HR \neq 1$$

Analysis Method

The same methods used for HF event in secondary objective #2 will be used for the AF endpoint here.

The crude cumulative incidence curves of AF endpoint will be displayed by treatment and NYHA class combinations using %CUMINCID:

```
%cumincid(data=AF, time=TtoAF, status=AFcens, event=1, compete=2, censored=0, strata=randNYHA)
```

where TtoAF starts from the date of randomization and ends at the date that the first >6 hrs of AF was reported in the device's Cardiac Compass Trends for those who experienced this event, or the date of death for those who died before experiencing a AF event, or the date of last documented follow-up (including the date of last available device data) for those who are censored. AFcens = 0 when a subject did not experience an AF event or death and therefore was censored; AFcens = 1 when a subject experienced an AF event the first time since randomization; AFcens = 2 when a subject died without experiencing an AF event. The competing risk of AF event exists when AFcens = 2.

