In addition, device measured AF burden and treatment for AF will be summarized. Device measured AF burden is defined as the daily time in AF as captured in Cardiac Compass averaged over all days with data. For AF reported as an adverse event, its symptoms and treatment taken documented in the CRFs will be listed.

The hypothesis regarding the aCRT effect on AF will be tested using a Cox proportional hazards regression model with a random site effect (frailty), stratified by NYHA class at enrollment. Section 4.3.2 has described this model in details. The analysis will be conducted using code similar to:

```
PROC PHREG DATA=AF;  
  CLASS NYHA site;  
  MODEL time*AF(0) = rand / TIES=efron;  
  STRATA NYHA;  
  RANDOM site/dist = gamma;  
RUN;
```

In these codes, AF = 1 given the occurrence of >6 hrs AF episode and AF = 0 otherwise; time to AF starts from the date of randomization and ends at the date when the first >6 hrs of AF was reported in the device's Cardiac Compass Trends for those who experienced this event, or the date of last documented follow-up or date of death for those who are censored.

The model assumptions will be checked using the same methods that are described in detail in section 4.3.2 for the primary endpoint. That is, the assumption of proportional hazards between the treatment arms will be checked by testing the significance of treatment by time interaction term; and, the assumption of constant hazard ratio for treatment across NYHA classes will be checked by testing the significance of treatment by NYHA class interaction and evaluating the hazard ratio for treatment within each NYHA class.

Missing Data

Non-informative censoring is assumed for lost to follow up in the analysis of defined AF event.

Secondary Competing Risk Analysis: Fine-Gray Regression

In addition to the Cox regression as the primary analysis for AF, Fine-Gray regression will be conducted as a secondary competing risk analysis.

Let $h_T(t)$ and $h_C(t)$ be the subdistribution hazard of $F_T(t)$ and $F_C(t)$, respectively. Under the Fine-Gray model¹⁴ that assumes proportional subdistribution hazards, $h_T(t) = \text{SHR} \cdot h_C(t)$, where SHR is the subdistribution hazard ratio of treatment compared to control for occurrence of the first >6 hrs AF episode. The null and alternative hypotheses are:

$$H_0 : \text{SHR} = 1$$

$$H_A : \text{SHR} \neq 1$$

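### The AF endpoint exists only in device data, but AF-free time at risk runs to the last documented contact, so time in which AF cannot be seen counts as AF-free

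*SAP*

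**What the plan says.** **Endpoint.** Protocol 11.5.1 states: "Incidence of AF will be determined from device data". SAP 4.4.4 makes this specific: "The endpoint will be the first day after randomization on which there is >6 hrs of AF reported in the" device's Cardiac Compass Trends. AF reported as an adverse event is only listed and does not count.

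**End of time at risk.** SAP 4.4.4 gives two versions for patients without AF. For the time variable used in the cumulative incidence and Fine-Gray analyses, time ends at death "or the date of last documented follow-up (including the date of last available device data) for those who are censored". For the Cox model that tests the hypothesis, it ends at AF "or the date of last documented follow-up or date of death for those who are censored".

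**What last documented follow-up means.** SAP 4.4.4 does not define it, but says "The same methods used for HF event in secondary objective #2 will be used for the AF endpoint here". SAP 4.3.2 reads: "Date of last documented follow-up since randomization is the maximum value among the dates of randomization". Section 4.4.2, whose methods AF borrows, repeats the list, which goes on to include "any study scheduled follow-up visit, exit, adverse event onset, adverse event resolved, system modification, and healthcare utilization".

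**Missing data.** The only rule is: "Non-informative censoring is assumed for lost to follow up in the analysis of defined AF event". Nothing covers a patient who is still in contact but whose device record has ended, or who has no device record.

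**The concern.** An event-free patient should be in the risk set only while the event could be detected. Here detection needs a device record, but the risk set is governed by visits, exit, adverse events, system modifications and healthcare use.

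The protocol foresees contact without device data:

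- Section 6.14 allows conditional disengagement with telephone follow-up, after which data collection requirements lapse.
- Section 6.15 asks for an exit interrogation only where available.
- Section 7 anticipates corrupted interrogation files.
- Section 3.6 makes remote monitoring optional.
- Section 8.3.1 asks for interrogation after death only when possible.

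Two things are at stake. The first is the absolute incidence of AF, which is understated in any arm that has gaps. The second is the hazard ratio, if gaps are more common or longer in one arm. AF is one of the seven secondary hypotheses in the Hommel procedure, so its p-value can also affect decisions on the others.

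**Working it through.** **Step 1: what the text does.** Let D be the last date with device data and C the latest of the listed contact dates. Under the Cox text, an AF-free survivor is censored at C. Under the other text, the date is max(C, D). Neither can fall before C. When C is later than D, the interval from D to C enters as AF-free although AF could not be recorded in it. If there is no D at all, the whole of C is AF-free time, because SAP 4.4.4 includes all randomized subjects.

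**Step 2: nothing to reproduce.** The documents state no AF event count, power or device-data coverage, so the size can only be illustrated.

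**Step 3: inputs.**

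- Control AF hazard, from the earlier trial in Protocol section 2 (16.2% of control patients; mean follow-up 20.2 months): h = −ln(1 − 0.162)/(20.2/12) = 0.105 per year. That trial used AF of more than 48 hours, not 6, so this is illustrative.
- Follow-up uniform from 3.5 to 7.5 years, from 4 years of enrollment plus 3.5 more (Protocol 11.3.4).
- Share of patients with a gap, f, and its length, g: assumed, 5% to 20% and 0.5 to 2 years.

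**Step 4: excess AF-free time.** Let A(g) be the mean probability of being AF-free g years before the end of follow-up:

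A(g) = [exp(−h(3.5 − g)) − exp(−h(7.5 − g))]/(4h)

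This gives A(0) = 0.565 and A(1) = 0.628. Observable time at risk per patient without gaps is (1 − 0.565)/0.105 = 4.14 years. A 1-year gap removes (0.628 − 0.565)/0.105 = 0.60 observable years per affected patient and puts in 0.628 × 1 falsely AF-free years.

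- f = 10%: 0.0628/(4.14 − 0.060) = 1.5% excess
- f = 20%: 0.1256/(4.14 − 0.119) = 3.1% excess

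The same formula gives 0.7% (f = 10%, g = 0.5) and 7.2% (f = 20%, g = 2). Simulation agrees. Over all scenarios run, excess time was about 0.5% to 7%, with the lowest values where 5% of one arm and 10% of the other had gaps.

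**Step 5: hazard ratio.** With no true effect, a 1-year gap in 10% of aCRT ON and 20% of aCRT OFF gives a rate ratio of 1.031/1.015 = 1.016. Cox fits (60,000 per arm; true HR 1.0, 0.8 and 0.54), each censored both ways, gave these ratios of the HR under the SAP rule to the HR censored at last device data:

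| Share with gap (ON / OFF) | 0.5 y | 1 y | 2 y |
|---|---|---|---|
| 10% / 10% or 20% / 20% | 1.000 | 1.000–1.001 | 1.000–1.003 |
| 5% / 10% | 1.003–1.004 | 1.007–1.008 | 1.017 |
| 10% / 20% | 1.007–1.008 | 1.015–1.017 | 1.035–1.037 |
| 20% / 10% | 0.993 | 0.985 | 0.965–0.969 |

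**The case against.** **Most gaps should be short.** Full interrogation is required at implant, randomization and every follow-up visit (Protocol 6.8 to 6.10), at system modifications (6.13), and at healthcare visits that change required programming (6.12). CareLink transmissions are collected where used. For a patient who attends, an adverse event or healthcare date can outrun the last interrogation by about one visit interval. Gaps of 1 to 2 years need missed visits or files, disengagement with continued contact, or explant. The documents give no frequency for these. This stands, and it limits the size.

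**The SAP partly recognises the issue.** Version 3.0 removed the conditional disengagement date from follow-up time as administrative, and 4.4.4 mentions the device-data date. The first change narrows one route, but later telephone-reported events can still extend the clock. The second shows awareness, but inside a maximum it cannot cap time at risk, and the Cox text omits it.

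**A reader might infer that the AF hazard ratio is materially biased.** The documents do not support that. Both arms share one visit and interrogation schedule, and equal gaps move the ratio by at most 0.3%. Unequal coverage is possible, since only subjects are blinded and control patients may have discretionary optimization, but nothing shows a two-fold difference.

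**A reader might also divide share times gap by about 4 years of follow-up.** That gives (0.20 − 0.10) × 1/4 = 2.5% for the 1-year, 10% versus 20% case. It is too high: patients with AF before the gap add no false time, and the 3.5 to 7.5 year range averages 5.5 years. The fitted shift is about 1.5% to 1.7%.

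**Conclusion.** As written, the rule is wrong rather than merely vague: following it counts unobservable time as AF-free, and the two descriptions in SAP 4.4.4 disagree on whether device dates matter. Cumulative incidence of AF is understated whenever gaps exist, even equal ones. For the hazard ratio the effect is negligible with equal gaps, and roughly 1% to 4% in either direction with gaps of 0.5 to 2 years in 10% versus 20% of patients. These sizes rest on assumed gap shares and lengths and on a hazard taken from a different AF definition. The primary endpoint is unaffected. The change should be made because it is cheap and is best settled before the treatment comparison is seen, not because a large bias has been shown.

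**What to change.** Use one rule in both places in SAP 4.4.4:

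1. Censor AF-free patients at the last date covered by Cardiac Compass data, in place of the last documented follow-up.
2. In the Cox model, also end time at risk at the last device data for patients who die later.
3. In the cumulative incidence and Fine-Gray analyses, keep death as a competing event when it falls within a pre-specified interval of the last device data, for example one scheduled visit interval. Otherwise censor at the last device data.
4. Patients with no post-randomization device data contribute no time at risk. Report their number, and device-data coverage, by arm. State how gaps inside a record are handled.

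Item 3 matters. Scheduled interrogations are six months apart from month 6 onward and post-mortem interrogation is not assured, so counting a death only when device data run up to it would turn many competing deaths into censorings and push estimated AF incidence upward. The interval leaves a short unobserved stretch before some deaths, which is the smaller fault.

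The cost is slightly less person-time, edits to two paragraphs and the death coding, and a little reprogramming. No new data collection is needed, because interrogation files already go to the sponsor (Protocol 6.10).

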4.4.5 Secondary Objective #5: Quality of life measured by KCCQ

The secondary objective #5 is to test the hypothesis that the change in quality of life, measured by the Kansas City Cardiomyopathy Questionnaire (KCCQ), in the aCRT ON group is better than the change in the aCRT OFF group

Hypothesis

The KCCQ questions are categorized into clinically relevant domains²⁰

- Physical limitation (question 1: 6 subquestions),
- Frequency of symptoms (questions 3, 5, 7 and 9),
- Severity of symptoms (questions 4, 6 and 8),
- Symptom stability (question 2),
- Self-efficacy and knowledge (questions 10 and 11),
- Social limitation (question 15: 4 subquestions) and
- Quality of life (questions 12, 13 and 14).

A score for each domain will be calculated. Also, total symptom score is the average of symptom frequency score and symptom severity score. In addition, two summary scores will be calculated:

- Clinical Summary Score: mean of physical limitation score and total symptom score;
- Overall Summary Score: mean of physical limitation score, total symptom score, quality of life score, and social limitation score.

Hypothesis testing will be performed on the overall summary score. Summary statistics will be provided for the other scores by study arm.

The KCCQ questionnaire is collected at baseline and at the 3, 6, 12, 18, and 24 months follow-up visits. The overall summary score (range, 0 to 100; higher scores indicate better health status) will be assessed. Let α_T and α_C denote the fixed treatment effect on KCCQ overall summary score for aCRT ON and aCRT OFF group, respectively. The null and alternative hypotheses are:

$$H_0 : \alpha_T = \alpha_C$$

$$H_A : \alpha_T \neq \alpha_C$$

Analysis Method

General linear mixed models will be used to analyze the continuous KCCQ overall summary score collected over time. In the primary analysis, the model will include the fixed effects of treatment, visit, treatment by visit interaction and baseline KCCQ score, and two random effects - random site effect and random subject effect:

$$Y_{ijk} = \mu + \alpha_i + \beta_j + \tau_{ij} + \lambda_{kg} + \gamma_k + \eta_{i(g)} + \varepsilon_{ijk}$$

Here:

- μ is the common intercept of the model
- α_i is the i th fixed treatment effect, $i=T, C$;
- β_j is the j th fixed visit effect, $j=1, 2, \dots, J$;
- τ_{ij} is the fixed interaction effect between i th treatment and j th visit;
- λ_{kg} is the fixed baseline KCCQ effect of g th subject in k th site;
- γ_k is the random site effect for the k th site, $k= 1, 2, \dots, K$;
- $\eta_{i(g)}$ is the random subject effect of g th subject in i th treatment group, $g=1, 2, \dots, G$;
- ε_{ijk} is the random error for the g th subject from k th site having i th treatment at j th visit.

The analysis will be conducted using the SAS MIXED procedure similar to below:

```
proc mixed data=KCCQ method=reml covtest;
  id pt;
  class pt site rand visit;
  model KCCQscore = rand visit rand*visit KCCQ_base
                / solution ddfm=satterth covb chisq;
  random site pt(rand);
run;
```

where KCCQscore is a continuous longitudinal endpoint that includes all post-randomization KCCQ measurements, visit is the categorical version of the visit number, rand*visit is the interaction between treatment and visit, and KCCQ_base is the KCCQ score at baseline. If the interaction between treatment and visit is not significant, it will be eliminated from the model and the main effect of treatment will be used to test the hypotheses; otherwise, if the treatment by visit interaction turns out to be significant, then treatment effect at each visit will be evaluated and the hypotheses will be tested using CONTRAST or LEMESTIMATE statement in the SAS MIXED procedure.

Missing Data

Missing data for individual KCCQ questions will be handled as suggested by the questionnaire authors¹⁹. Missing values within each domain are assigned the average of the answered items within that same domain. Scale scores are transformed to a 0 to 100 range by subtracting the lowest possible scale score, dividing by the range of the scale and multiplying by 100.

To investigate whether patients with missing KCCQ data are missing at random (MAR), the baseline characteristics between patients with missing data on KCCQ and those with complete data will be compared. If there is no evidence to suggest that patient data are not missing at random, we will cautiously conclude that patient data are MAR. Then, multiple imputation techniques will be employed to account for missing data.

Multiple imputation^{21 22} models will be developed to estimate the overall scores for all subjects/visits with missing overall scores. Imputation may be stratified if differences are detected in baseline characteristics between those with or without missing data. The SAS MI and MIANALYZE procedures will be used to conduct multiple imputation.

Determination of Patients/Data for Analysis

The analysis follows the ITT principle and includes all the randomized subjects.

